Study Protocol and Statistical Analysis Plan

(Version: 2.0 Date: 2023.3.28)

Name: Construction of Symptom Network in Maintenance Hemodialysis Patients

Applicant: Ren Ji Hospital, Shanghai Jiao Tong University School of Medicine

Principal investigator: [name]

Objective

Through a cross-sectional questionnaire survey, a general information questionnaire and Dialysis Frequency, Severity, and Symptom Burden Index were used to investigate the frequency, severity, and degree of symptom distress in MHD patients, and to analyze the differences in symptom distress status between long and short dialysis age MHD patients. Using the R 4.2.2 software qgraph package, construct symptom networks for MHD patients of long and short dialysis age through network analysis. Analyze network centrality indicators, including intensity, closeness centrality, and mediation centrality, to identify core symptoms and compare if there are any differences between the two groups, aiming to lay the foundation for precise and efficient phased symptom management.

Background

End stage renal disease (ESRD) is caused by various kidney diseases, leading to irreversible decline in renal function. The main renal replacement therapy (RRT) for ESRD is hemodialysis (HD), peritoneal dialysis (PD), and kidney transplantation. Due to the impact of kidney supply on kidney transplantation, it is limited in clinical practice, and hemodialysis has become the most common method of RRT in most countries. According to the registration system of the Chinese Research Data Services (CNRDS), as of the end of 2021, there were 751098 dialysis patients and 155738 new patients in China, with an average dialysis age of 50.9 months. The proportion of patients with dialysis age greater than 5 years was 31.5%. There are a large number of hemodialysis patients with a longer dialysis age.

With the continuous development of dialysis technology, the survival rate of maintenance hemodialysis (MHD) patients is becoming higher and higher. However, MHD patients may experience various symptoms during long-term treatment, which is the main cause of discomfort and physical and mental health for patients. The physical and mental pain or torment experienced by patients due to the disease itself and/or the symptoms caused by treatment is called symptom distress. Multiple studies have shown that the incidence of symptom distress in MHD patients ranges from

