management measures for depression in clinical practice. Han et al. constructed symptom networks for autism and schizophrenia. Yang Hongli et al. applied symptom networks to HIV infected individuals and identified fatigue as the core symptom. They suggested that when HIV infected individuals have multiple symptoms at the same time, high-intensity and precise intervention on fatigue can reduce the transmission of fatigue as a mediating bridge in the symptom network, reduce the severity of fatigue symptoms, and also alleviate the severity of other symptoms. As mentioned above, symptom network analysis can identify core symptoms, and changing these core symptoms may be an important entry point for changing the entire network. In practical clinical work, implementing key interventions by nurses on core symptoms can more effectively improve other related symptoms and improve intervention efficiency. Applying symptom networks to the field of symptom management is a promising and precise technology in real-world clinical settings.

This study has developed a symptom distress questionnaire for maintenance hemodialysis patients. Previous literature on symptom distress and symptom management in MHD patients has been reviewed. Whether there are differences in symptom distress among MHD patients of different dialysis ages, and how to identify the core symptoms of MHD patients of different dialysis ages through symptom networks to improve the accuracy and effectiveness of intervention are all directions that need to be studied in the future. The research hypotheses of this study are: ① There are differences in the frequency, severity, and degree of symptom distress between long and short dialysis age MHD patients; ② By using network analysis methods to construct symptom networks for long and short dialysis age MHD patients, identify the core symptoms of different dialysis age MHD patients. Based on literature review and clinical experience, it is assumed that the core symptoms of long dialysis age MHD patients are itching or dry skin, while the core symptoms of short dialysis age MHD patients are fatigue or dry mouth.

Contents

1. Current survey of symptom burden in maintenance hemodialysis patients

① Understanding the current status of symptom distress in maintenance hemodialysis patients through cross-sectional questionnaire survey

② Comparative analysis of symptom distress in maintenance hemodialysis patients with long and short dialysis age

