2. Construction of symptom network and core symptom recognition for maintenance hemodialysis patients

① A multicenter study on the current status of symptom distress in maintenance hemodialysis patients

② Construct symptom networks for long-term, short-term, and all maintenance hemodialysis patients using network analysis based on cross-sectional survey data from multiple centers

③ Identify and analyze the core symptoms of long dialysis age, short dialysis age, and all maintenance hemodialysis patients based on network centrality parameters

Methods

Participants

Convenient sampling method was used to select MHD patients from six blood purification centers, including the East, West, South, Baoshan Branch, Ningbo Hangzhou Bay Branch, and Punan Hospital of Renji Hospital Affiliated to Shanghai Jiao Tong University School of Medicine.

(1) Inclusion criteria: ① Age not less than 18 years old; ② Regular hemodialysis time greater than or equal to 3 months; ③ The dialysis plan did not change within one month; ④ Informed consent and voluntary participation in this study.

(2) Exclusion criteria: ① Previous or current mental illness; ② Cognitive impairment; ③ Acute cardiovascular and cerebrovascular disease; ④ Acute infection period; ⑤ Complications such as severe cerebrovascular sequelae and tumors.

(3) Sample size and calculation method: The Dialysis Frequency, Severity, and Symptom Burden Index for dialysis patients used in this study includes a total of 30 symptoms. When constructing a symptom network model, the threshold parameters

that need to be estimated are 30, paired association parameters are $30 \times \frac{(30-1)}{2} = 435$, and the total parameters are $30 + 435 = 465$. Therefore, the sample size needs to be at least 465. Considering 10% of invalid samples, the sample size of this study is at least $465 \div (1 - 10\%) = 517$.

Instruments

General Information Questionnaire: Designed by the researchers themselves, including laboratory examination indicators such as gender, age, dialysis age, marital status, educational level, work status, residential status, medical expense payment method, economic burden, primary disease, comorbidities, recent medication, hemoglobin, etc.

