Dialysis Frequency, Severity, and Symptom Burden Index(DFSSBI) : DFSSBI is an adaptation of the Dialysis Symptom Index (DSI) developed by Weisbord et al., using the symptom management theory model as the theoretical framework, by American scholars Danquah et al., which increases the frequency of symptoms and the degree of distress in two dimensions. This scale has been proven to have good reliability and validity in foreign countries. Cronbach's α The coefficient is 0.923, the content validity coefficient is 0.939, and the retest reliability is 0.83. It has good internal consistency, stability reliability, and structural validity. The scale consists of 30 items, including 25 physiological symptoms such as fatigue, dry skin, itching, etc; Psychological symptoms include sadness, irritability, tension, etc., totaling 5 symptoms. The appearance of symptoms is obtained in the form of "having" and "not having". The frequency and severity of occurrence are evaluated using a Likert 4 level score, with values ranging from "occasional/mild" to "always/very" ranging from 1-4 points. The degree of distress is evaluated using a Likert 5 level score, with values ranging from 0-4 points from "no impact" to "very serious" ranging from 0-360 points. The higher the score, the heavier the individual's burden of symptoms. Zhou Xiaojuan et al. used the Chinese version of DFSSBI to investigate the symptom burden of hemodialysis patients, and their Cronbach's α The coefficient is 0.89, and the retest reliability is 0.91, indicating that the scale is suitable for application in domestic

hemodialysis patients.

Data Collection

Before the investigation, obtain the consent of the hospital ethics committee and departments, explain and communicate with the survey subjects. On dialysis day, researchers will use unified guidelines to explain the research purpose and explain the answer methods and precautions for each question to the survey subjects. The questionnaire is filled out by the patient themselves. For survey subjects who are unable to independently complete the questionnaire, the researcher can collect data through one-on-one Q&A. Collect and check for any missing items on the spot, and promptly supplement and complete them.

Statistical Analysis Plan

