Enter the collected information into the database established by Epidata 3.1, and after verification, import it into SPSS 21.0 software for data analysis. The patient's gender, marital status, education level, work status, and other counting data are described using frequency and percentage. Age, hemoglobin, blood phosphorus, and other measuring data that meet normality are represented by mean and standard deviation, while those that do not meet normality are represented by median and interquartile spacing. The symptom distress scores of MHD patients with different characteristics were tested for normality and homogeneity of variance. If they obey the normal distribution and have the same variance, t-test and analysis of variance were used. Otherwise, nonparametric rank sum test was used. Use R4.2.2 software qgraph package for network analysis to generate complex network descriptions of the relationship between symptoms. Use network centrality indicators such as strength, tight centrality, and mediation centrality to represent the degree of interconnection of symptom networks. The intensity reflects the total direct connection between symptoms and other symptoms, that is, the ability of symptoms to affect other symptoms; The closeness centrality reflects the reciprocal of the distance between symptoms and other symptoms, that is, the core position of symptoms in the network; Mediation centrality reflects the number of shortest paths through the symptom, which serves as a bridge between the symptoms in the network.

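### Core symptoms are to be identified and compared between dialysis-age groups, but the network analysis has no uncertainty measure, no between-group test and no index that decides which symptom is core

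*Combined protocol and SAP*

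**What the plan says.** The Objective uses strength, closeness and betweenness (there called intensity, closeness and mediation centrality) "to identify core symptoms and compare if there are any differences between the two groups". It gives the intended use of that comparison as "aiming to lay the foundation for precise and efficient phased symptom management". The research hypotheses at the end of the Background are specific. For the long group, "it is assumed that the core symptoms of long dialysis age MHD patients are itching or dry skin". The prediction for the short group is a different pair: "while the core symptoms of short dialysis age MHD patients are fatigue or dry mouth". Under Contents, item 2③ has the task: "Identify and analyze the core symptoms of long dialysis age, short dialysis age, and all maintenance hemodialysis patients based on network centrality parameters". It names no single index.

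The Statistical Analysis Plan turns this into qgraph in R 4.2.2 and one instruction: "Use network centrality indicators such as strength, tight centrality, and mediation centrality to represent the degree of interconnection of symptom networks". It then says what each index reflects: strength is the total direct connection, closeness is the symptom's core position, and betweenness is its role as a bridge. The only group tests (t-test, analysis of variance, rank sum test) are for symptom distress scores.

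Two other places bear on which network is meant. Under Participants, the sample-size paragraph counts threshold parameters "that need to be estimated are 30, paired association parameters are" 435. Under Instruments, each symptom has a presence item and ratings of frequency, severity and distress, with a total "ranging from 0-360 points".

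**The concern.** A comparison of core symptoms needs three things: a rule for what is core, a measure of how well each group's ranking is determined, and a way to judge whether the groups differ by more than chance. The plan has none of them for the networks. Three indices can point to three symptoms, and nothing says which prevails. The estimator and the symptom score entering the network are also open, and both affect the ranking.

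At stake is the aim that the Objective attaches to the comparison, namely symptom management by phase of dialysis. Two samples from the same network can have different top symptoms. If that is read as a difference between phases, the management built on it rests on noise.

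**Working it through.** **The plan's own figure.** With 30 symptoms there are 30 thresholds and 30 × 29 / 2 = 435 pairs, so 30 + 435 = 465. Then 465 / (1 − 0.10) = 516.7, rounded up to 517. The stated sample size reproduces. It is a parameter count for one network and contains no error rate, power or effect size for a comparison.

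**What the count implies.** One threshold per symptom fits a binary pairwise model. The instrument's maximum is 30 symptoms × 3 ratings × 4 points = 360, so binary presence is only one of several possible scores. A 0-4 score in an ordinal model would have 4 × 30 = 120 thresholds, and 120 + 435 = 555 parameters. The Statistical Analysis Plan does not say which score or model is used.

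**Group sizes (assumption).** The documents give no expected group sizes. Applying the national share with dialysis age above 5 years (31.5%, Background) to 465 valid patients gives 0.315 × 465 = 146 long and 319 short.

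**Item correlation (assumption).** If the two Cronbach's alphas under Instruments are over k = 30 items, then r = α / (k − (k − 1)α):
- α = 0.89: 0.89 / (30 − 25.81) = 0.212
- α = 0.923: 0.923 / (30 − 26.767) = 0.285

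If alpha was taken over all 90 ratings, the implied mean would mix several ratings of the same symptom. It would not be a between-symptom correlation, so no such value is derived here.

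**Illustration.** Both groups have the same true 30-symptom network, with 0-4 scores. Splits of 465 are 146/319, 186/279 and 232/233, with 400 pairs of samples per cell. The lead is the top true strength divided by the second. The table shows how often the top-strength symptom differed between groups.

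| Estimator | No clear leader (up to 1.10×) | Lead 1.25× | Lead 1.5× |
|---|---|---|---|
| Correlation, item correlation 0.21-0.29 | 89-93% | 0.5-25% | 0% |
| Unregularised partial correlation, item correlation 0.08-0.29 | 93-98% | 78-89% | 63-83% |

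Other assumptions move these rates:
- Another set of true networks without a clear leader gave 55-62% for the correlation network.
- A simpler one-factor model at latent correlation 0.21 gave 93-96%, 28-38% and 0-0.5% across the three correlation columns.
- At an assumed item correlation of 0.08-0.12, even a 1.5× lead gave 8-52%.
- A binary pairwise model (146/319 only) gave 94-97% with no leader and 16-71% at leads of 2.6-3.3×.

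Lasso networks were not simulated, so no rate is claimed for them.

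**What bootstrap reporting would show.** In a correlation network at 0.21, the observed leader ranked first in a median of 31% / 34% of bootstrap samples (n = 146 / 319) with no lead, 57% / 90% at 1.25×, and 100% / 100% at 1.5×. With partial correlations the shares were 15% / 19%, 17% / 24% and 16% / 32%.

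**Why a relative contrast.** Suppose both groups share the same core symptom (lead 1.25×) but differ in overall correlation (0.285 against 0.212). A permutation test of absolute strength for the four hypothesised symptoms, Holm-adjusted, then rejected in 43-60% of runs. The same test on strength divided by the group's mean strength rejected in 1.5-7.5%. The upper end came with the higher correlation moved to the other group, so control was not exact in that setting. These tests used correlation networks only.

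**The case against.** The strongest reply is that this is a descriptive, cross-sectional study. Asking whether groups differ can mean setting two rankings side by side, and the plan states no confirmatory network claim or error rate. That stands in part: the rankings may be reported as descriptive. But the Objective asks whether the groups differ, the Background states a hypothesis, and the result is meant to support phased management.

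Second, closeness may be the deciding index, since it is the one described as the core position. That is a gloss on one of three indices; the Objective and Contents use centrality parameters jointly. The wording does need reconciling. It is also true that the list of indices is introduced by *such as* and is not closed, but no other index is named and an open list gives no decision rule.

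Third, the simulated rates run from 0% to 98% with assumed leads and models, and they count any change of top symptom. This objection stands against precise use of them. A reader might infer that the second hypothesis would be wrongly supported more than 90% of the time. The figures do not show that. Wrong support needs itching or dry skin to lead in the long group and fatigue or dry mouth in the short group. With 30 equal contenders that chance is (2/30)² = 0.4%, and with only those four contending equally it is (2/4)² = 25%.

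**Conclusion.** The gap is in the text and holds without any simulation: for the networks there is no uncertainty measure, no between-group test and no deciding index. As written, two rankings would decide the comparison. Rankings can agree or disagree with the hypothesis, but they cannot show that a difference exceeds sampling noise.

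The size is known only in direction. Chance disagreement on the top symptom is usual when none clearly leads. It is rare in a correlation network with a strong leader at item correlations of 0.21-0.29, and it stays frequent with unregularised partial correlations. This rests on the assumed 31.5% split, alpha over 30 items, and invented true networks.

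Two stronger readings are not supported. One is that the plan has no between-group tests at all: it tests symptom distress scores. The other is that the observed core symptoms will be spurious: that depends on the true lead and the estimator, which the documents do not give. The point is a cheap improvement.

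**What to change.** Write into the Statistical Analysis Plan before analysis:

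1. One index that decides core (strength is a reasonable choice), with the core-position wording for closeness reconciled and the other indices reported descriptively. Name one estimator and one symptom score, the same in both groups, and reconcile them with the 30 + 435 parameter count.
2. In each group, bootstrap intervals for that index and case-dropping stability. Leading symptoms that are not separated are listed as not distinguishable.
3. A permutation test that shuffles group labels at the actual group sizes and refits both networks (for score-based networks, scores standardised within group first). Contrast each symptom's strength relative to its group's mean strength, and report global strength alongside. Either test all 30 symptoms with multiplicity control, or make the four hypothesised symptoms the primary family and the other 26 (30 − 4), including any other observed leader, a secondary adjusted family. Testing the four alone would leave any other leader untested, although Contents seeks core symptoms without restriction.
4. A claim of different core symptoms only when the bootstrap and permutation results support it; otherwise the rankings are reported as descriptive.

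The cost is some R code and computing time, with no new data. The study may have to report no demonstrable difference, above all in the smaller group or with partial correlations. The estimator is a real trade-off: in the illustrations correlation networks gave steadier rankings, but they do not separate direct from indirect links, while the plan describes strength as direct connection.

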13.75% to 91.5%, which is at a high level. Symptom distress is negatively correlated with the quality of life of MHD patients. Excessive symptom distress increases the cost of treatment and exacerbates the psychological burden on patients. Persistent symptom burden can significantly affect the quality of life of MHD patients and increase their mortality rate. MHD patients suffer from multiple symptoms at the same time. Li Jiuhong et al.'s research results show that MHD patients experience a total of 3-25 (13.12 ± 5.27) symptoms, which is similar to Weisbord et al.'s average of 9 symptoms. MHD patients experience a wide variety of symptoms, and how to accurately and effectively manage symptoms is the future research direction.

With the prolongation of dialysis treatment time for patients, some urea toxin that cannot be completely cleared by dialysis accumulates in the patient's body, which is closely related to discomfort symptoms such as itching, joint pain, and difficulty falling asleep. Ran Yuli et al. found that the dialysis age of MHD patients is negatively correlated with their physical function and role. With the prolongation of dialysis age, the physiological function of MHD patients will decrease to varying degrees, and various disease-related complications will also occur. The focus of symptom management will shift accordingly. Conducting grouping studies based on dialysis age for MHD patients has certain clinical significance. At present, domestic scholars use a 5-year hemodialysis period as the boundary, dividing dialysis age >5 years into long dialysis age, and dialysis age ≤ 5 years into short dialysis age. Hu Qian and others set up symptom management consultants to develop symptom management pathways and guide responsible nurses to implement symptom management for patients according to the pathway table. The results indicate that setting up symptom management consultants can reduce the incidence of symptoms in MHD patients, improve their quality of life, and improve patient satisfaction. A meta-analysis showed that aerobic exercise can improve several symptoms related to hemodialysis in adults receiving MHD, including restless leg syndrome, depressive symptoms, muscle spasms, and fatigue. Zhao Ying et al. used air wave pressure therapy to prevent dialysis related muscle spasms, Zuo et al. managed symptoms of fatigue through nurse led non drug multidisciplinary holistic care, Beerappa et al. improved sleep

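### Long and short dialysis-age networks are to be compared on centrality with no named estimator, no set group sizes and no between-network test, so unequal groups can make identical networks look different

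*Combined protocol and SAP*

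**What the plan says.** The Objective is to build networks for long and short dialysis age and use centrality to "identify core symptoms and compare if there are any differences between the two groups". The Background gives the grouping: "dividing dialysis age >5 years into long dialysis age, and dialysis age ≤ 5 years into short dialysis age". Under Contents, part 2, separate networks are planned for long, short and all patients, with core symptoms read from the centrality parameters.

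The Statistical Analysis Plan says: "Use network centrality indicators such as strength, tight centrality, and mediation centrality to represent the degree of interconnection of symptom networks". Here tight centrality is closeness and mediation centrality is betweenness. Strength is defined there as a symptom's total direct connection to the others.

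On size, Methods, Participants, item (3) gives one figure for the whole sample: "Therefore, the sample size needs to be at least 465", raised to 517 for invalid questionnaires. Recruitment is by convenience: "Convenient sampling method was used to select MHD patients from six blood purification centers". No quota or minimum per group is given. The only figure that bears on the split is a national registry value in the Background: "The proportion of patients with dialysis age greater than 5 years was 31.5"%.

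The plan names the qgraph package. It does not state the edge type, regularisation, tuning, a between-network test, an adjustment for group size or a stability check.

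**The concern.** Strength is a total of edge sizes, conventionally taken without sign. Sampling error in an edge therefore does not cancel: it adds to the total, and adds more when the group is smaller. Closeness is built from the same edge sizes. A penalised estimator can work the other way, because a smaller group is shrunk harder and loses more edges. Either way the level of the index carries a component set by sample size and estimator. An interval around each group's own value would not remove it, because the interval is centred on a shifted value.

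The SAP reads these indices as a measure of how interconnected a network is, and comparing the two groups is a stated aim. If the groups are unequal, a reported difference in interconnection could reflect group size and an undocumented software setting rather than dialysis age. The study is meant to support symptom management by dialysis phase, so such a difference could be carried into practice.

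**Working it through.** **Inputs from the documents.** The scale "includes a total of 30 symptoms". Minimum valid N is 465, with a 10% allowance. Distress items are scored 0 to 4 (Instruments). The 31.5% share is a registry figure, used here only as an assumed split.

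**The plan's own figure.** 30 + 30 × 29/2 = 30 + 435 = 465, and 465/0.9 = 516.7, rounded up to 517. This reproduces.

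**Assumed split.** 465 × 0.315 = 146.5 and 465 × 0.685 = 318.5, about 146 v 319. For 517: 162.9 and 354.1, about 163 v 354. The ratio is 0.685/0.315 = 2.17.

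**Closed form, no true links, unregularised partial correlations.** The standard error of an edge is about 1/√(n − 29):
- n = 146: 1/√117 = 0.0925
- n = 319: 1/√290 = 0.0587

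Expected strength is 29 × √(2/π) × SE, with √(2/π) = 0.798:
- n = 146: 29 × 0.798 × 0.0925 = 2.14
- n = 319: 29 × 0.798 × 0.0587 = 1.36

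The ratio is √(290/117) = 1.57. This is an extreme case, since real symptoms are linked.

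**Simulation A: identical true networks, 25% of edges present, all positive, mean correlation about 0.3.** With unregularised partial correlations at 146 v 319, strength was 1.35 times and closeness 1.30 times higher in the smaller group. Of 30 symptoms, 28 looked stronger there (15 expected by chance). The count was 21.5 at 200 v 265 and 14.7 at 146 v 146. EBIC graphical lasso with gamma 0.5 reversed the sign; with gamma 0 there was no bias. A repeat gave a strength ratio of 1.34 for partial correlations and about 1.02 for plain correlations.

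**Simulation B: identical true networks, 15% of edges present, partial correlations 0.08 to 0.30, continuous or skewed 0–4 items, 163 v 354.**

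| Estimator | Strength, long/short | Closeness, long/short | Runs with long group higher on strength |
|---|---|---|---|
| Plain correlation | 1.06–1.11 | 1.09–1.14 | 72–82% |
| Unregularised partial correlation | 1.35–1.39 | 1.25–1.32 | 100% |
| EBIC lasso, gamma 0.5 | 0.41 (continuous), 0.05 (0–4 items) | often zero or undefined | about 2% |

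At 258 v 259 the strength ratio was 0.97 to 1.01 for all three estimators, which isolates group size as the cause.

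**Sensitivity (partial correlations, N = 517).** The strength ratio is 1.88 at a 20% long share, 1.39 at 31.5%, 1.18 at 40% and 1.00 at 50%. At N = 1000 and 31.5% it is still 1.30.

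**Which symptom ranks first (simulation B).** With identical networks the two groups agreed on the top-strength symptom in 10–53% of runs at 163 v 354, and in only 12–67% at 258 v 259. The rank correlation of strength between groups was 0.32 v 0.38 (partial) and 0.76 v 0.83 (plain), unequal v equal sizes.

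**Two possible remedies, tested on identical networks.**
- *Equal-size random subsets of the larger group.* These put the levels on one scale (ratio 1.00). Used as a test, they fail: 11% of symptoms fell outside the 95% subset range at 146 v 319, and about 30% at 200 v 265, against 5% nominal. The subsets overlap heavily, and the smaller group's own error is ignored.
- *Label permutation at the observed sizes.* For global strength at 163 v 354 the estimated type I error was 0.065 (200 runs; Monte Carlo SE about 0.015–0.017), compatible with 0.05. Per symptom it held about 5%.

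**The case against.** The strongest reply is that the plan never says raw strength or closeness will be set side by side. The Objective, the Contents and the second hypothesis all ask which symptoms are core in each group. That is a within-network ranking, and a roughly common inflation of all 30 values need not change the ranking. This stands in part. Imbalance matters far less for rankings than for levels, and the level comparison is one reading of the aim. It is a natural reading, however, because the SAP interprets the indices as degree of interconnection. The ranking reading has its own gap: nothing in the plan separates a real difference in the top symptom from chance.

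Three stronger inferences are tempting, and the documents do not support them.

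- *The groups will be about 1:2.* The 31.5% is registry background. A convenience sample from six centres may split differently, and 465 and 517 are minimums.
- *A false difference will arise, with the long group looking more connected.* Size and direction depend on an estimator the plan does not name. The sample-size count includes 30 thresholds, which a Gaussian partial-correlation network does not have, so that section does not settle the choice either.
- *Imbalance is what makes core symptoms differ.* The top symptom differs often at equal sizes too. The main cause is few patients per network.

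**Conclusion.** The concern holds in a limited form. The plan compares two networks on indices whose levels depend on group size, and it has no named estimator, no set group sizes and no between-network test. If the groups are unequal, identical networks can appear to differ in interconnection.

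At an assumed 146 v 319, the illustrative size is strength about 1.35 times higher in the smaller group with unregularised partial correlations. The effect is reversed, and can be much larger, with EBIC graphical lasso at gamma 0.5. With plain correlations it is about 1.02 to 1.11 across the networks and sizes tried. It is absent near 50:50. A different top symptom in the two groups is not, on its own, evidence of a real difference at any split.

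The simulated figures rest on assumed true networks and item distributions, which the documents do not give. Betweenness and networks of binary present/absent items were not examined.

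**What to change.** Amend the Statistical Analysis Plan before analysis:

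1. State that raw strength and closeness values from the two groups are not compared by eye.
2. Fix the estimator, edge type and tuning in advance, use the same settings in both groups, and report both group sizes.
3. Base any claim of a between-group difference, in global strength or in a symptom's centrality, on a label-permutation test. Keep the observed group sizes in every permutation. Judge the observed difference against the permutation distribution itself, whose centre need not be zero when the groups are unequal.
4. Correct for 30 symptoms: uncorrected, 30 × 0.05 = 1.5 false differences are expected per index. With a Bonferroni-type first step at 0.05/30 = 0.00167 and a smallest attainable p-value of 1/(B + 1), at least B = 599 permutations are needed, and preferably well above that.
5. Equal-size random subsets of the larger group may be used to describe index levels on one scale. Their spread must not be used as a significance test.

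The cost is SAP wording and a little more analysis. Data collection does not change and all patients are kept. The downside is that fewer apparent differences will be declared.
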